16.4.1 Mayo Scoring System

All components of Mayo scoring system (RB, SF, ES and PGA) as well as three Mayo scores (MMS, MCS and PMS) will be listed by visit. RB and SF will be summarized by visit.

16.5 Symptomatic Remission Sensitivity Analyses

Ten endpoints having a direct relationship to Symptomatic Remission will be subjected to an additional sensitivity analysis in which the way Stool Frequency (SF) is handled is altered:

- Primary definition: “Stool frequency (SF) subscore = 0 or 1”
- Sensitivity analysis definition: “Stool frequency (SF) subscore = 0 (or = 1 with a ≥ 1 -point decrease from baseline)”

The ten endpoints subjected to this sensitivity analysis are given in Table 8:

Table 8. Symptomatic Remission Sensitivity Analyses

Endpoint	Definition	Sensitivity Analysis Derivation
Primary Endpoint	Proportion of participants with clinical remission at Week 13 using modified Mayo score (MMS)	Stool frequency (SF) subscore = 0 (or = 1 with a ≥ 1 -point decrease from baseline), RB subscore = 0, and endoscopic subscore (ES) ≤ 1 (excluding friability)
Key Secondary	Proportion of participants with symptomatic remission at Week 13	SF = 0 (or = 1 with a ≥ 1 -point decrease from baseline), and RB subscore = 0
Other Secondary Endpoint	Proportion of participants with endoscopic and clinical remission at Week 13	ES = 0, SF subscore = 0 (or = 1 with a ≥ 1 -point decrease from baseline), and RB subscore = 0
Other Secondary Endpoint	Proportion of participants with endoscopic remission, histologic remission, and clinical remission at Week 13	ES = 0, Geboes Index score < 2.0, SF subscore = 0 (or = 1 with a ≥ 1 -point decrease from baseline), and RB subscore = 0
Other Secondary Endpoint	Proportion of participants with symptomatic remission at Weeks 4, 8, 10	SF = 0 (or = 1 with a ≥ 1 -point decrease from baseline), and RB subscore = 0
Other Secondary Endpoint	Proportion of participants with clinical remission at Week 13 using total Mayo Clinic score (MCS)	Stool frequency (SF) subscore = 0 (or = 1 with a ≥ 1 -point decrease from baseline), RB subscore = 0, endoscopic subscore (ES) ≤ 1 (excluding friability), PGA ≤ 1 , and SF + RB + ES + PGA ≤ 2
Exploratory	Proportion of participants with clinical remission at Week 52 using modified Mayo score (MMS)	Stool frequency (SF) subscore = 0 (or = 1 with a ≥ 1 -point decrease from baseline), RB subscore = 0, and endoscopic subscore (ES) ≤ 1 (excluding friability)

Endpoint	Definition	Sensitivity Analysis Derivation
Exploratory	Proportion of participants with clinical remission at both Weeks 13 and 52 using modified Mayo score (MMS)	Stool frequency (SF) subscore = 0 (or = 1 with a ≥ 1 -point decrease from baseline), RB subscore = 0, and endoscopic subscore (ES) ≤ 1 (excluding friability)
Exploratory	Proportion of participants with symptomatic remission at Week 18, Week 26, Week 36, and Week 52 (separately)	SF = 0 (or = 1 with a ≥ 1 -point decrease from baseline), and RB subscore = 0
Exploratory	Proportion of participants with endoscopic and clinical remission after 52 weeks of treatment	ES = 0, SF subscore = 0 (or = 1 with a ≥ 1 -point decrease from baseline), and RB subscore = 0

No imputation will be performed for these sensitivity analyses, non-responders will be handled as defined at the beginning of [Section 16](#), FAS will be used, and these analyses will use the same CMH statistical methodology with randomized stratification factors as other responder analyses. VTX002 60 mg vs Placebo will be handled separately from VTX002 30 mg vs Placebo.

16.6 Pharmacokinetics Analysis and Plasma Concentration

See [Section 29](#).

17. SAFETY

17.1 Adverse Events

17.1.1 General Considerations

Adverse events are collected from the date and time of signing ICF and will be coded according to the MedDRA version 26.0 or higher. Adverse events with an onset prior to first dose of study treatment are collected as part of medical history. Adverse events with an onset on or after first dose of study treatment are collected on adverse event eCRFs. All AE tables will be summarized according to the actual treatment group with an appropriate safety set.

A treatment-emergent adverse event (TEAE) is either an AE occurring on or after the date and time of first study treatment intake, or an ongoing AE worsening in severity after the date and time of the first study treatment. If an AE date coincides with the date of first dose of study treatment and either the AE onset time or drug administration time is missing then the AE will be considered treatment-emergent. AEs having both start and end dates missing will also be considered treatment-emergent. AEs with a missing onset date and non-missing end date will be considered as TEAE unless end date is prior to the first drug administration. Adverse events with missing seriousness will be considered serious. Adverse events with missing severity will be considered to have CTCAE grade 3. Adverse events with missing relatedness will be considered related.

AEs with an onset prior to the date and time of first study treatment intake (i.e., during Screening) will be listed but will not be summarized unless they either result in a TEAE due to AE worsening in severity or are serious. TEAE summaries will be separately prepared for study periods of Induction Treatment Period, LTE, OLE, and for the entire study:

- TEAEs with an onset on or after date and time of first study treatment intake during the Induction Treatment Period but prior to last participation in the Induction Treatment Period will be associated with Induction. Also, TEAEs resulting from worsening of severity during Induction in an AE having onset during Screening will be associated with Induction. Summaries for the Induction Treatment Period will use the Safety Set. This set of TEAEs will be associated with the Induction Period Analysis.
- TEAEs with an onset on or after the date and time of first study treatment intake during the LTE but prior to last participation in LTE will be associated with LTE. Also, TEAEs resulting from worsening of severity during LTE in an AE having onset prior to LTE will be associated with LTE. Summaries for the LTE will use the Safety-ET Set.
- TEAEs with an onset on or after the date and time of first study treatment intake during OLE but prior to last participation in OLE will be associated with OLE. Also, TEAEs resulting from worsening of severity during OLE in an AE having onset prior to OLE will be associated with OLE. Summaries for the LTE will use the Safety-ET Set.
- TEAEs with an onset on or after the date and time of first study treatment intake will be used for entire-study AE summarization. Note that a TEAE may also be an AE having onset during Screening for this purpose, but having worsening severity at some point after first study treatment intake. An AE considered as TEAE because of worsening severity will only be counted once, at maximum severity, for this purpose. Summaries for the entire study will use the Safety-ET Set.

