Safety-Extension Treatment (Safety-ET) Set: The Safety-ET Set includes all participants who received at least 1 dose of study treatment in the LTE or the OLE Treatment Periods. The Safety-ET Set will be used for all safety analyses. In general, participants will be analyzed according to actual study treatment dose in Safety-ET analyses. Additional details are provided for specific analyses described elsewhere in this SAP.

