11.2 Protocol Deviations

After the last participant completes the Induction Treatment Period, the protocol deviation log for the Induction Treatment Period will be provided to Sponsor for review at the final Induction Treatment Period Blinded Data Review Meeting (BDRM). Sponsor will classify protocol deviations as either major or minor per the Protocol Deviation Plan (PDP).

Similarly, at the end of the study, the final project-level protocol deviation log will be provided to the sponsor prior to the final database lock. Upon the study end, the final project-level protocol deviation log will be approved by the sponsor at the final study BDRM and filed in trial master file (TMF).

For the Induction Treatment Period, major deviations will be separately summarized (number and percentage) by treatment group for the FAS according to the following categories, and all deviations will be listed:

- Withdrawal criteria
- Randomization procedure

- Subject visit completion or timing
- Study procedure or assessment
- Study medication
- (Serious) AE reporting
- Other

Note that participants experiencing an intercurrent event during the Induction Treatment Period and not experiencing other deviations preventing contribution to the primary and key secondary analyses of the primary and key secondary endpoints will be included in the PP set and treated as non-responders in those analyses.

A separate summary will be provided for protocol deviations occurring during the entire study. The FAS-ET set and planned treatment group will be used for this purpose.

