14.2 OTHER MEDICATIONS

Medications not taken for Ulcerative Colitis will be considered prior medications if the end date of the medication is prior to the date of first dose of study treatment. Otherwise, they are considered concomitant medications.

A medication is considered concomitant for the Induction Treatment Period if it meets the following conditions:

- a) Medication started or was ongoing on or after the first study treatment administration date
and
- b) Medication started or was ongoing on or before Visit 7
or
Medication started or was ongoing on or before any of the Early Termination/1-Week Follow-up/2-Week Follow-up visits for participants that permanently discontinue study treatment during the Induction Treatment Period (and are therefore discontinued from the study).

A medication is considered concomitant for the entire study if meets the following conditions:

- c) Medication started or was ongoing on or after the first study treatment administration date
and
- d) Medication study treatment was ongoing on or before the two-week follow-up visit.

Imputation rules specified in Section 10.1 will be applied to partial/missing dates.

Three summaries will be created:

- Prior medications will be summarized by planned treatment group and overall for the FAS, mFAS, and PP sets.
- Concomitant medications taken during the Induction Treatment Period will be summarized by planned treatment group and overall for the Safety, FAS mFAS, and PP sets. This summary will be generated for the Induction Period Analysis.

- Concomitant medications taken during the entire study summaries will be summarized by planned treatment group and overall for FAS ET and PP populations. This summary will be generated at study end.

Additionally, the use of P-gp or BCRP transporters during the study will be flagged in participant-level dataset(s) and in listings. Please see [Section 25](#) (Appendix IV) for WHO Drug Dictionary (WHODD) ATC codes specifying P-gp and BCRP transporters.

If prior medications for UC are inadvertently entered on eCRF pages intended for concomitant medications, these records will be treated as prior medications.

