For entire study summaries, if the same TEAE is reported for the same participant more than once, the TEAE is counted only once, at the date of TEAE onset, for each SOC, PT and study treatment combination. For entire study summary purposes, study treatment shall be considered the same in each study period as what is used for TEAE summaries by study period, and a TEAE having onset in a given study period will be linked to the treatment associated with that study period.

Separate listings will be prepared for all AEs, SAEs, AEs leading to study treatment interruption, AEs leading to permanent discontinuation of study treatment and AEs leading to death, with flags for TEAE (Y/N).

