17.6 Optical Coherence Tomography

Four summaries will be prepared: for Induction Treatment Period (Safety Set), LTE, OLE, and overall, using the Safety and Safety-ET sets.

Shift tables from baseline ('Normal', 'Abnormal, not clinically significant' and 'Abnormal, clinically significant') to each visit will be provided. Denominator will be the number of participants in treatment group with non-missing results at specified visit.

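### Entire-study adverse event tables run on the Safety-ET Set, so they leave out everyone who never entered an extension, including all who stopped treatment permanently in Induction

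*SAP*

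**What the plan says.** SAP 17.1.1 plans adverse event summaries for Induction, the LTE, the OLE and the entire study. For Induction it states: "Summaries for the Induction Treatment Period will use the Safety Set". The entire-study item takes in all treatment-emergent events from the first intake of study treatment, including Screening events that worsen later, and ends: "Summaries for the entire study will use the Safety-ET Set".

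SAP Section 8 defines that set: "The Safety-ET Set includes all participants who received at least 1 dose of study treatment in the LTE or the OLE Treatment Periods". Protocol 9.3 has the same definition. The Safety Set, by contrast, is every randomized participant with at least one dose.

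On early stoppers, SAP 14.2 refers to "participants that permanently discontinue study treatment during the Induction Treatment Period (and are therefore discontinued from the study".

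Two other entire-study summaries use the matching efficacy extension set. For protocol deviations, SAP 11.2 says: "The FAS-ET set and planned treatment group will be used for this purpose". For medications, SAP 14.2 says: "Concomitant medications taken during the entire study summaries will be summarized by planned treatment group and overall for FAS ET and PP populations". For OCT, SAP 17.6 lists the summaries for "LTE, OLE, and overall, using the Safety and Safety-ET sets", and SAP 17.7 does the same for pulmonary function.

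**The concern.** The scope of the entire-study tables and the set assigned to them do not match. The scope starts at the first Induction dose, while the set admits only people who went on to receive an extension dose. Membership is thus decided after treatment starts and depends on having come through Induction, so those who tolerated treatment worst are the ones removed.

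SAP 17.1.2 plans entire-study tables of SAEs, of events leading to discontinuation and of events leading to death. These are the tables a reader would use for the overall safety picture. Protocol 7.1 requires permanent discontinuation for certain cardiac events around first dosing, for confirmed clinically significant macular edema and for a marked fall in pulmonary function. A participant stopped in Induction for any of these would be missing from the entire-study table. Induction events in participants who later enter an extension do stay in it.

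**Working it through.** **Set membership.** The point rests on definitions, and the plan gives no figure to reproduce.

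1. Events in scope: all treatment-emergent events from first intake (SAP 17.1.1, entire-study item).
2. Set used: at least one dose in the LTE or OLE (SAP Section 8; Protocol 9.3). SAP Section 8 also says the extension sets are subsets of the Induction sets.
3. Route into an extension: the Week 13 visit must be completed (Protocol 4.1.3 and 4.1.4; SAP 4.1.4.1 for participants under Protocol version 1). For Week 13 non-responders the OLE is optional, so some completers may never enter.
4. Permanent discontinuation of treatment in Induction means leaving the study (SAP 14.2).

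From 2 to 4, a participant who permanently stops in Induction is in the Safety Set and cannot be in Safety-ET. Completers who decline the OLE are outside it too. SAP 17.1.1 otherwise asks only for an appropriate safety set, which does not override the specific assignment.

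**Number dropped.** Planned N is 189, or 63 per arm (SAP 4.1). All randomized participants are assumed to be dosed. The documents do not give the proportion who never enter an extension. The middle value below borrows the 10% dropout figure from SAP Section 6 and 16.1.4.1 and is not a forecast.

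| Assumed non-entry | Dropped, of 189 | Dropped per arm, of 63 | Safety-ET N |
|---|---|---|---|
| 5% | 189 × 0.05 = 9.45 | 3.15 | 180 |
| 10% | 189 × 0.10 = 18.9 | 6.3 | 170 |
| 15% | 189 × 0.15 = 28.35 | 9.45 | 161 |

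**Effect on a discontinuation table.** Let *a* participants stop because of an event in Induction and *b* in an extension. No one counted in *a* is in Safety-ET, so:

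- Induction table (Safety Set): *a*/189
- entire study as written (Safety-ET): *b*/N of Safety-ET
- entire study on the Safety Set: (*a* + *b*)/189

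With assumed counts and 10% non-entry:

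| *a*, *b* | Induction table | Entire study as written | Entire study, Safety Set |
|---|---|---|---|
| 9, 5 | 9/189 = 4.8% | 5/170 = 2.9% | 14/189 = 7.4% |
| 4, 2 | 4/189 = 2.1% | 2/170 = 1.2% | 6/189 = 3.2% |

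For the 9, 5 case, the as-written figure is 5/180 = 2.8% at 5% non-entry and 5/161 = 3.1% at 15%, so it depends little on that assumption. Whenever *b* < *a*, the entire-study count is below the Induction count. That cannot happen on the Safety Set, because *a* + *b* is at least *a*.

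**The case against.** The strongest reply is that nothing is hidden. The Induction tables use the Safety Set, the listings in SAP 17.1.2 cover all adverse events, and SAP 11.1 tabulates discontinuation reasons and deaths by period with percentages based on the number randomized. This stands as a limit on the harm. It does not make the pooled tables right.

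The wording may be a drafting slip. The OLE item in SAP 17.1.1 ends by naming the LTE, which suggests a closing sentence copied from one item to the next. That is plausible, but a programmer following the text would still use Safety-ET. Similarly, SAP Section 2 says the plan covers the Induction period, yet Sections 5.2 and 17 specify the entire-study outputs, so this wording governs them.

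Protocol 9.4.5 says participants who stop treatment are followed like the others, which sits uneasily with the remark in SAP 14.2. But Safety-ET requires an extension dose, and follow-up alone does not supply one. The zero share would fail only if someone were dosed again after a permanent discontinuation.

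The percentages pool the three arms and use invented counts, whereas the tables are by treatment. That is fair: they show direction and rough scale, and the set-membership argument does not need them. Likewise, two tables on different declared sets do not strictly contradict each other. A reader would still be puzzled by an entire-study count lower than the count for one of its periods.

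**Conclusion.** The concern holds: the rule as written gives a wrong result. Entire-study adverse event tables on Safety-ET exclude every treated participant without an extension dose. For events leading to permanent discontinuation in Induction, the share kept is zero, given no later re-dosing. Deaths before any extension dose are lost in the same way, as are the other Induction events of participants who never enter an extension. How many participants this removes is unknown; 9 to 28 of 189 corresponds to the assumed 5% to 15%.

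The entire-study protocol-deviation summary has the same fault through FAS-ET, as does the FAS-ET version of the entire-study medication summary, for which a Per Protocol version is also planned. The fault is confined to pooled outputs produced at study end. The Induction safety tables, the listings, and the primary and key secondary analyses are untouched. It should be fixed, but it does not threaten the trial's main conclusions.

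**What to change.** In SAP 17.1.1, assign the entire-study adverse event summaries to the Safety Set and keep Safety-ET for the LTE and OLE summaries.

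State the denominator of each treatment column, for example all participants who ever received that treatment. This is needed because SAP 17.1.2 says "a TEAE having onset in a given study period will be linked to the treatment associated with that study period", and a participant can change treatment on entering the OLE and so contribute to two columns.

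In SAP 11.2 and 14.2, replace FAS-ET with the FAS for the entire-study protocol-deviation and concomitant-medication summaries.

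As housekeeping in the same edit, name a set for the entire-study laboratory summary (17.2.3) and the overall ECG presentation (17.5.1). The overall OCT and pulmonary function summaries already include the Safety Set among those named and need no change of set.

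The cost is a few lines of SAP text and a changed population flag in the entire-study table programs, made before final database lock. Nothing in the Induction Period Analysis has to be rerun.

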17.1.2 TEAE Summaries

An overall TEAE summary table will be presented separately for each of the study periods described in [Section 17.1.1](#). It will include the number and percentage of participants with at least one event of specified category. The following categories will be displayed:

- TEAE
- Treatment-emergent serious AE (SAE)
- Non-serious TEAEs
- TEAE/treatment-emergent SAE related to study treatment
- AE/TEAE leading to death.
- TEAEs Grade 4 or higher
- TEAEs Grade 3 or higher

- TEAEs Grade 2 or higher
- TEAEs leading to study treatment discontinuation
- TEAEs leading to study treatment interruption
- TEAEs by maximum CTCAE severity
- Related TEAEs by maximum CTCAE severity

The incidence of treatment-emergent SAEs, TEAEs, and non-serious TEAEs will be summarized separately, by the following, for each of the study periods described in [Section 17.1.1](#):

- SOC and PT, ordered by descending frequency of PT in VTX002 60 mg group
- SOC, PT, and relatedness to study treatment, ordered by decreasing frequency in VTX002 60 mg group
- SOC, PT, and maximum Common Terminology Criteria for Adverse Events (CTCAE) toxicity grade and ordered by decreasing frequency in VTX002 60 mg group.
- PT, ordered by descending frequency of PT in VTX002 60 mg group

Additionally, the incidence of treatment-related TEAEs, treatment-related SAEs, treatment-related non-serious TEAEs, TEAEs leading to study treatment interruption, TEAEs leading to premature discontinuation of study treatment, and TEAEs leading to death will be summarized separately, by SOC and PT, for each of the four types of TEAE summaries described in [Section 17.1.1](#) and ordered by descending frequency of PT in VTX002 60 mg group.

In summaries associated with a specific study period – either Induction, LTE, or OLE – if the same TEAE is reported for the same participant more than once, the TEAE is counted only once for each SOC by PT combination. In these study period tabulations, study treatment shall be considered to be the treatment a study participant actually receives during a given study period. If a study participant receives multiple study treatments during a given study period, adverse events for that participant will be tabulated according to the highest dose of study treatment received.

For entire study summaries, if the same TEAE is reported for the same participant more than once, the TEAE is counted only once, at the date of TEAE onset, for each SOC, PT and study treatment combination. For entire study summary purposes, study treatment shall be considered the same in each study period as what is used for TEAE summaries by study period, and a TEAE having onset in a given study period will be linked to the treatment associated with that study period.

Separate listings will be prepared for all AEs, SAEs, AEs leading to study treatment interruption, AEs leading to permanent discontinuation of study treatment and AEs leading to death, with flags for TEAE (Y/N).

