4.0 STUDY DESIGN

4.1 Overall Design

This is a multicenter, randomized, double-blind, placebo-controlled study to evaluate the efficacy and safety of VTX002 30 mg and 60 mg in participants with moderately to severely active UC following daily oral administration of VTX002 as a tablet. Approximately 189 eligible participants will be randomized in a 1:1:1 ratio to receive VTX002 30 mg, VTX002 60 mg, or matching placebo, once daily (approximately 63 participants per treatment group).

The target patient population will include the following categories:

- Patients who have had an inadequate response, loss of response, or intolerance to conventional therapy and are naïve to biologic/JAK inhibitors (conventional failed)
- Patients who have had an inadequate response, loss of response, or intolerance to a biologic/JAK inhibitor (biologic/JAK inhibitor failed). Patients in this category may have received prior conventional therapy. It is expected that approximately 35% of participants in the study will have had an inadequate response to biologics.

Participant randomization will be stratified based on (a) biologic/JAK inhibitor prior use status (Yes or No) and (b) baseline corticosteroid use (Yes or No), and (c) baseline disease activity (MMS 5-6 or 7-9).

As shown in [Figure 1](#), the study consists of a 28-day Screening Period, a 13-week double-blind Induction Treatment Period (including 7 days of titration followed by 12 weeks of treatment at the assigned dose), an LTE Treatment Period of up to 39 weeks, an OLE Treatment Period of up to 143 weeks, and a 2-week Follow-Up Period. The maximal duration of treatment including the Induction Period, LTE and OLE will be 36 months.

The duration of study participation for each participant is planned to be approximately 162 weeks, and the total duration of the study is planned to be approximately 60 months. Approximately 120 study centers in 15 countries are expected to participate in this study.

The Schedule of Activities (SoA) for the study is provided in [Section 1.2](#).

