9.4.3 Safety Analyses

All safety data (eg, Holter ECG monitoring, 12-lead ECG, OCT, PFT, and PE) will be listed and summarized using descriptive statistics. Separate summaries of safety data will be provided for the Induction, the LTE, and the OLE Treatment Periods. Additional details regarding analyses of the safety data (eg, Holter ECG monitoring, 12-lead ECG, OCT, PFT, and PE) will be provided in the SAP.

Treatment-emergent AEs are defined as AEs that first occurred or worsened in severity after the first administration of study treatment and prior to 30 days after the last administration of study treatment.

Adverse events will be coded using the Medical Dictionary for Regulatory Activities. For each study treatment, numbers of TEAEs and incidence rates will be tabulated by Preferred Term and System Organ Class.

Treatment-emergent AEs by maximum severity, TEAEs by relationship to study treatment, SAEs, TEAEs leading to death, and TEAEs leading to discontinuation of study treatment will be tabulated for each treatment group. Commonly occurring TEAEs in either treatment group will be summarized using descriptive statistics.

All central laboratory test results, vital signs measurements, ECG results, and weight measurements will be summarized for each treatment group using descriptive statistics at each visit for raw numbers and change from baseline. The incidence of treatment-emergent abnormal laboratory, vital sign, and ECG values will also be summarized using descriptive statistics.

Incidence of AEs including pulmonary dysfunction and macular edema, as well as abnormalities in clinical laboratory assessments, vital signs, Holter ECG monitoring, 12-lead ECG, and PE will also be summarized.

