9. GENERAL CONSIDERATIONS

9.1 Summary Statistics

In general, continuous variables will be summarized using the following standard descriptive summary statistics: number of observations, mean, standard deviation (SD), minimum, first quartile, median, third quartile, maximum, and number of missing observations. Use of decimal places in descriptive statistics will be as follows:

- Min, Max: same as the actual data (but not more than 4 decimals)

- Mean, Geometric Mean, Median, First Quartile, Third Quartile: actual data + 1 decimal (but not more than 4 decimals)
- SD, Geometric SD: actual data + 2 decimals (but not more than 4 decimals)
- Geometric CV: 2 decimals (but not more than 4 decimals)

Categorical data will be described using frequency counts and percentage. Percentages will be based on the number of participants in the selected analysis set and relevant treatment group unless otherwise stated. Percentages will be rounded to one decimal place except for one hundred percent, which will be presented as 100%. Tests will use a two-sided alpha=0.05 unless otherwise specified.

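### Entire-study adverse-event tables show crude percentages by treatment although 60 mg accrues far more follow-up than placebo, so uncommon events could look about 2 to 6 times more frequent on 60 mg with no drug effect

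*SAP*

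**What the plan says.** SAP 17.1.1: "TEAE summaries will be separately prepared for study periods of Induction Treatment Period, LTE, OLE, and for the entire study". On the last of these: "Summaries for the entire study will use the Safety-ET Set". That set requires a dose in the LTE or OLE (SAP 8), so participants who stopped during Induction are not in it.

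SAP 17.1.2 on the overall table: "It will include the number and percentage of participants with at least one event of specified category". The general denominator rule in SAP 9.1 counts people, not time: "Percentages will be based on the number of participants in the selected analysis set and relevant treatment group unless otherwise stated".

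For the entire-study tables, "a TEAE having onset in a given study period will be linked to the treatment associated with that study period". Repeats of an event in one participant collapse within a treatment but not across treatments. A participant who moves from placebo to the OLE can therefore contribute events under both.

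The periods differ in length. Induction is 13 weeks in every arm. Week 13 responders continue their assigned treatment for up to 39 more weeks (Protocol 4.1.3). All OLE treatment is 60 mg (SAP 4.3.3), and Protocol 4.1 allows "an OLE Treatment Period of up to 143 weeks".

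Protocol 9.4.3 states that "numbers of TEAEs and incidence rates will be tabulated by Preferred Term and System Organ Class", but it defines no time denominator. SAP 15.1 summarizes exposure duration separately and does not link it to the adverse-event tables.

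**The concern.** A crude percentage with at least one event rises with time at risk. When one column holds up to 52 weeks per participant and another holds up to 156, the difference between them mixes treatment with length of follow-up.

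Safety through the LTE and OLE is a stated objective (Protocol 3.1), and the 13-week table cannot address it. The distortion is largest for uncommon events that accumulate over time. Several Targeted Medical Events in SAP 17.1.3, such as malignancies and serious or opportunistic infections, are plausibly of that kind. A reader of the entire-study table could see a harm that is not there, or dismiss a real one as longer follow-up.

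The LTE tables share the problem to a smaller extent, because participants who lose response may leave for the OLE, so time in the LTE depends on outcome. The documents give no basis for putting a figure on that.

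**Working it through.** **Period arithmetic.** The SAP's own maximum for Week 13 non-responders is reproduced: 13 + 143 = 156 weeks (SAP 4.1.4.2). The Protocol cap of 36 months agrees: 36 × 365.25 / 12 / 7 = 156.5 weeks. SAP 4.1.4.3 instead gives 13 + 39 + 143 = 195 weeks for participants entering the OLE from the LTE. The placebo maximum is 13 + 39 = 52 weeks, and a placebo non-responder who enters the OLE has 13.

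**Null model.** Every treatment has the same constant hazard h per participant-year, so there is no drug effect. A participant with w weeks on a treatment shows an event there with probability 1 − exp(−h·w/52). A column percentage is the average of this over everyone in the Safety-ET Set who was ever on that treatment. That denominator is my assumption, because SAP 17.1.2 does not state one. Arms are 63 each and total treatment is capped at 156 weeks.

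**A case that can be checked by hand.** Suppose everyone responds, completes the LTE and completes the OLE to the cap. Placebo has 52 weeks each. The 60 mg column has 104, 104 and 156 weeks from the placebo, 30 mg and 60 mg arms, a mean of 364/3 = 121.3. At h = 0.10:

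- Placebo: 1 − exp(−0.1) = 9.5%
- 60 mg: [2 × (1 − exp(−0.2)) + (1 − exp(−0.3))] / 3 = (2 × 18.1% + 25.9%) / 3 = 20.7%
- Ratio: 2.18

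**Scenarios with attrition.** The documents do not give response, loss of response, OLE uptake or dropout, so these are assumptions set out as a range. Loss of response is placed 20 weeks into the LTE, and later OLE dropout halfway through the remaining time.

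| Scenario | Week 13 response, placebo/30/60 mg | LTE loss | OLE uptake | Non-responders stopping at OLE Week 13 | Later OLE dropout | Mean weeks, placebo vs 60 mg |
|---|---|---|---|---|---|---|
| A, full completion | 100/100/100% | 0% | 100% | 0% | 0% | 52.0 vs 121.3 |
| B, middle | 35/55/60% | 30% | 90% | 40% | 30% | 25.5 vs 95.6 |
| C, low contrast | 50/55/60% | 10% | 70% | 60% | 50% | 34.8 vs 76.0 |
| D, high contrast | 25/55/60% | 50% | 95% | 20% | 15% | 20.7 vs 116.3 |

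Crude percentages, 60 mg vs placebo, with their ratio:

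| h per participant-year | A | B | C | D |
|---|---|---|---|---|
| 0.01 | 2.3 vs 1.0% (2.32) | 1.8 vs 0.5% (3.72) | 1.4 vs 0.7% (2.17) | 2.2 vs 0.4% (5.57) |
| 0.10 | 20.7 vs 9.5% (2.18) | 16.4 vs 4.7% (3.47) | 13.2 vs 6.4% (2.06) | 19.7 vs 3.9% (5.11) |
| 1.0 | 89.3 vs 63.2% (1.41) | 74.3 vs 35.7% (2.08) | 66.7 vs 45.3% (1.47) | 82.9 vs 30.7% (2.70) |
| 3.0 | 99.8 vs 95.0% (1.05) | 91.3 vs 67.5% (1.35) | 88.7 vs 77.0% (1.15) | 95.3 vs 62.5% (1.53) |

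The ratio exceeds 1 in every cell. It runs from 2.06 to 5.57 at h of 0.10 or less, and from 1.05 to 2.70 at h of 1 to 3, where percentages saturate. First events per participant-year give a ratio of 1.00 throughout. That follows by construction from the constant hazard and shows only that the measure removes the effect of follow-up length.

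**The case against.** The best defence is that the randomized safety comparison is already planned. The Induction table uses the Safety Set over the same planned 13 weeks in every arm. The entire-study tables come at study end as descriptive summaries (SAP 5.2), SAP 17.1 plans no between-treatment test of adverse events, and SAP 2 describes the document as covering Induction reporting. All of that stands and limits the harm. Even so, SAP 17.1.1 and 17.1.2 do prescribe the LTE, OLE and entire-study tables, and treatment columns set side by side will be compared.

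A reader might infer a 10-fold excess by setting a 60 mg participant at 156 weeks against a placebo non-responder at 13 (25.9% vs 2.5% at h = 0.10). The documents do not support that reading. The tables compare columns, not individual extremes. Participants from the placebo and 30 mg arms can have at most 143 weeks on 60 mg. The OLE Week 13 stop shortens 60 mg time further, as does the 39-week OLE for Protocol v.1 participants who did not re-consent (SAP 4.1.4.1). Nor does the excess apply to every row: common categories saturate, and front-loaded events such as first-dose heart-rate effects (Protocol 2.2.2.5) would be inflated less than a constant hazard implies.

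The Protocol's mention of incidence rates is weak evidence of a conflict with the SAP, since no time denominator is given. The mock tables (SAP 19 and 20) are not available to us and may settle the denominator. Finally, only Week 13 responders enter the LTE and the OLE is not randomized, so rates per participant-year would still carry responder selection and differences in time since first dose.

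**Conclusion.** The point holds for the entire-study tables and, to a lesser and unquantified degree, for the LTE tables. As written, the plan gives columns in which treatment and follow-up time cannot be separated. With no drug effect, the 60 mg to placebo ratio of percentages would be about 2 to 6 for events at or below about 0.1 per participant-year and about 1.05 to 2.7 for common categories. This rests on an equal constant hazard, the assumed flow through the periods, a 156-week cap, and a denominator of Safety-ET participants ever on the treatment.

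It would be wrong to conclude that the safety tables as a whole can neither show nor exclude a dose effect. The Induction table is unaffected and supports a fair comparison over 13 weeks. The OLE table is all 60 mg and makes no comparison between doses. The remedy is a cheap improvement to later descriptive output and leaves the Induction Period Analysis untouched.

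**What to change.** - In the LTE, OLE and entire-study tables, add participant-years at risk and first events per 100 participant-years with 95% CI, by treatment received at onset. Do this for any TEAE, SAEs, discontinuations and each Targeted Medical Event.
- State in SAP 17.1.2 the entire-study denominator for participants counted under more than one treatment.
- State that between-treatment safety comparison rests on the Induction table, and label the extension rates descriptive and non-randomized.
- Reconcile the 195 weeks in SAP 4.1.4.3 with the 156 weeks in SAP 4.1.4.2 and the 36-month cap in Protocol 4.1.

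The cost is some added programming. SAP 15.1.1 already derives first and last treatment dates for each period. One new rule is needed: SAP 17.1.1 counts events with both dates missing as treatment-emergent, while SAP 10.1 leaves such dates unimputed, so the plan must say how they enter time to first event.
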